### **Potential Risks of the Study:**

- 1 Risk: Breach of confidentiality  
Likelihood of risk: Rare  
Seriousness to the subject: Minimal
2. Risk: Saliva collection. There is a risk of choking on salivette chewing swab.  
Likelihood of risk: Rare  
Seriousness to the subject: Serious
3. Risk: Actigraphy. Minimal risks exist with actigraphy. It is possible that participants may experience some discomfort from the band.  
Likelihood of risk: Infrequent  
Seriousness to the subject: Minimal
4. Risk: Clinical interview and questionnaires. Participants may feel psychological discomfort when being interviewed or completing questionnaires related to their insomnia, mood, or health.  
Likelihood of risk: Rare  
Seriousness to the subject: Minimal
5. Risk: Melatonin side effects. The safety of melatonin has been well-documented in both animal and human studies, with no studies showing evidence of serious adverse events from melatonin. Possible side effects include drowsiness, headache, dizziness, or nausea.  
Likelihood of risk: Infrequent  
Seriousness: Minimal

### **Potential Benefits:**

Potential benefits of the proposed research to the participants include an active treatment for DSWPD, thus many can expect to experience improvement in their sleep and related functioning during the day. The study could potentially identify a more effective treatment for DSWPD than the current standard of care. Additionally, we will have other treatment referral services in place in the event that we identify other potential sleep disorders, such as insomnia. Thus, the risks associated with participating are reasonable in light of the potential benefits to the participants and others.

### ***Protection against Study Risks***

Informed Consent Process. All subjects will provide written informed consent prior to beginning participation in the study. The consent process will inform potential subjects about the study, indicates that their participation is voluntary, and they have the right to stop participation at any time. Risks are enumerated in the informed consent form and described orally during the consent process.

#### Protection Against Risks.

Melatonin side effects: To minimize side effects from melatonin, a very small dose of melatonin (0.5 mgs) is utilized in the study, and for a short period of time (28 days). Further, individuals who take medications for which there are known interactions with melatonin, or who have medical conditions for which melatonin is contraindicated, will be excluded from participation in the study. Participants will be provided with written and verbal instructions to avoid driving or operating heavy machinery until they know how the melatonin will affect their alertness.

Saliva sample collection: Participants will be shown how to use the saliva collection swab to minimize the risk of choking.

Actigraphy: Participants will be instructed on how to dry the band should it become wet to minimize discomfort.

Violation of Confidentiality: To minimize the risk to confidentiality, we will ensure that data are protected and coded only by subject identification number. Further, only highly trained study team members will be interacting with participants or have access to study data. These protections are likely to be very effective in preventing loss of confidentiality.

Psychological discomfort: To minimize this risk, all interviews and questionnaire completion will be completed by skilled research staff in private offices. Participants will also be informed that they do not have to answer every question to participate in the study.

Although we do not anticipate screening or enrolling participants who are at risk for suicide, should the participant report suicidal ideation (on interview, the Patient Health Questionnaire-9, or in clinical interaction or any other study interaction), participants will be further screened for suicide risk using the Columbia Suicide Severity Rating Scale (C-SSRS). Note that the majority of cases in our current and previous research studies are generally determined to be minimal risk- no immediate threat to self or others, no plan in place, no means to carry out threat, etc. For minimal risk cases (positive answers to questions 1 or 2 on C-SSRS suicidal ideation scale with negative answers to questions 3-5), staff will express concern to the participant and provide resources (including a pamphlet from the National Suicide Prevention Lifeline, the phone number for Michigan Medicine Psychiatric Emergency Services), and referral information for treatment depending on the situation. For moderate risk (positive answers to question 3 on C-SSRS with negative answers to questions 4 and 5) or high/imminent risk (positive answers to questions 4 or 5 on C-SSRS) cases, [name] (PI) will be immediately paged for consultation; Drs. [name] and [name] (Co-Is) may also be paged if [name] is unavailable/as necessary. For

moderate and high/imminent risk cases, staff will first discuss their concerns with the participant and ask their permission to arrange a liaison with study staff (i.e., as noted above, Drs. [name], [name], or [name]) for further assessment. If the participant refuses consultation, staff and the on-call supervisor determine safety plans and resources and notify medical staff and/or authorities in some cases.

**Table 2. Study-Specific AE Reporting Timeline**

Reportable Events	Timing of Report to IRB and FDA
Unanticipated problem involving risks to subjects or others related to this research study	Serious: within 7 days Non-serious: with scheduled continuing review
Any physical, social, or psychological harm attributable to participation in this research study (e.g., an injury occurring during a study visit, infection at the site of a blood draw if antibiotics are required)	Serious: within 7 days Non-serious: with scheduled continuing review
Death while on study regardless of relatedness	Within 7 days
Privacy violation or breach of confidentiality	Within 7 days
Protocol deviations not related to an adverse event	With scheduled continuing review
Unanticipated problem related to the research that is not a serious adverse event	With scheduled continuing review
Expected, minor side effects commonly associated with melatonin use: 

• Dizziness

• Sleepiness

• Headache

• Nausea

• Transient depression

• Insomnia

• Nightmares or vivid dreams

• Diarrhea

• Irritability

	With scheduled continuing review
Other serious events not attributable to the research except death as noted above	With scheduled continuing review

## **9. DATA ANALYSIS/STATISTICAL METHODS**

### **9.1 Sample Size Determination**

We based our sample size estimation on the number of participants necessary to detect a 1 h change in DLMO; the sample size required to detect this change at 90% power with an alpha of 0.05 is 23 per group. Thus, our proposed sample of 25 participants per group (50 total) should be adequate to detect a clinically meaningful change in DLMO.

### **9.2 Data Analysis**

Descriptive analyses will be completed by graphical and numerical summarization of key variables. Treatment groups will be compared on pre-treatment demographic and clinical variables using t-tests, chi-square tests, and Fisher's exact tests as appropriate. Variables that emerge as potential confounders from this analysis will be controlled for in the final analyses. Weekly averages will be calculated for total sleep time, initial sleep latency, sleep onset time, and sleep offset time for each week of the study for both actigraphy and sleep diary.

#### ***9.2.1 Analysis of Primary Endpoint***

Change in DLMO from pre- to post-treatment will be calculated in minutes for each participant. A 2-tailed t-test will evaluate the difference between the change in DLMO between the two groups.

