### **Dim light melatonin onset can be readily measured in the field**

The time of melatonin onset in dim light (or dim light melatonin onset; DLMO) is the gold standard circadian marker (Lewy et al. 1989) and most reliable circadian phase marker in humans (Klerman et al. 2002). Dim light melatonin onset can be obtained via blood, urine, or saliva; advantages of saliva relative to other methods include practicality and reliability (Benloucif et al. 2008). Historically, research utilizing DLMO has been conducted in laboratory settings, which limits clinical utility. However, our group has pioneered the development of, and established the validity for, a kit for home-based saliva sampling to measure DLMO in the field. [name] (Co-I) has developed a novel in-home DLMO kit, which she has validated against laboratory DLMOs, with a very high correlation between the in-home and in-laboratory DLMOs ( $r = 0.91$ ,  $p < 0.001$ ), and excellent compliance, as 92% of the in-home samples were valid ([name] et al. 2015). Crucially, [name] has also validated the kit in adults with DSWPD, with high correlations ( $r = 0.93$ ,  $p < 0.001$ ) relative to in-laboratory DLMOs and high compliance, as 83% of the in-home samples were valid ([name] et al. 2016). In conjunction with [name], [name] (PI) has used the in-home DLMO kit with postpartum women with depression, with excellent compliance (98% of the DLMOs were valid; ([name] et al. 2017)).

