### **2.2.1 Primary Endpoint**

The primary endpoint is change in time of DLMO from pre- to post-treatment.

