## 5 STUDY TREATMENTS

### 5.1 Allocation to Treatment

Eligible participants will be randomized using the minimization method (Pocock et al. 1975) in a 1:1 ratio to M-DLMO or E-DLMO. Assignment to condition will be balanced by age and baseline sleep onset time on free days. For allocation of participants, a computer program (the Treatment Assignment System, created by UM's Consulting for Statistics, Computing, and Analytics Research) will be used by the study coordinator to generate the group assignment at enrollment for each participant.

Participants will be blinded to the specific study hypotheses and to their group assignment. The study clinician will be blinded to group assignment. The study coordinator, who communicates the time of melatonin administration to the study clinician, will not be blinded to the actual DLMO of participants in the M-DLMO condition; however, they will be blinded to the actual DLMO of participants in the E-DLMO condition until their participation is complete.

Due to individual variation in melatonin levels or errors in the saliva collection process, it is possible that DLMO will not be able to be determined for a small proportion of participants. To retain these participants in the protocol, if they are randomly assigned to the M-DLMO condition, the study coordinator may change their assignment to the E-DLMO condition. Data for these participants will be examined post-hoc upon completion of the study using sensitivity analyses before determining whether to retain or discard their data from analyses.

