## 7.1 Primary Endpoint Assessments

Protocol activity and assessments are summarized in Table 1 above.

Primary endpoint: change in the time of DLMO from pre- to post-treatment.

To assess time of DLMO, all eligible participants (regardless of group assignment) will undergo in-home salivary DLMO collection at pre- and post-treatment, using the protocol established by [name] (Co-I) ([name] et al. 2015). Participants will be oriented to the collection procedures during their clinic visit. Participants will be in dim light starting 30 minutes prior to the first sample collection. Collection begins 6 hours prior to participants' habitual sleep onset per their most recent week of actigraphy at baseline. At post-treatment, collection begins 6 hours prior to participants' bed time as assigned at the final treatment session. Samples are collected via Salivette every 30 minutes until bedtime (13 samples total). They are provided with a kit, which includes: a checklist of procedures; a test tube rack; a toothbrush; a nightlight; blue-blocking Uvex glasses (with an Actiwatch attached to monitor compliance of use); an iPod programmed to alarm at collection times; a light medallion (an Actiwatch with light sensor worn around the neck to monitor compliance with light exposure); Salivette collection vials equipped with Track Cap, which will record when the vial was opened; and a label dispenser with pre-labeled labels. Participants wear the blue-blocking glasses throughout the dim light saliva collection and are required to remain seated in the 10 minutes before each sample. When the iPod alarms, participants brush their teeth without toothpaste, collect saliva by chewing on the Salivette, and deposit it in the vial. Participants are informed about the compliance measures utilized in the study. Samples will be stored in participants' freezers until they can be transported to our facility. Samples are centrifuged for two minutes, frozen, and assayed using Bühlmann Laboratory radioimmunoassay (ALPCO Diagnostics, Salem, NH) at **Solidphase Inc.** To ensure consistency and to minimize the effects of sleep schedule changes on the weekends/days off of work, whenever possible, all participants will complete DLMO collection on the third night of their typical workday sleep schedule (e.g., DLMO collection will occur on a Wednesday, Thursday, or Friday night for participants who work a traditional Monday-Friday schedule).

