### **12.2 Institutional Review Board (IRB)**

Before implementing this study, the protocol, the proposed informed consent form and other information to be provided to subjects, must be reviewed by a properly constituted Institutional Review Board (IRB). Any amendments to the protocol must be reviewed and approved by IRBMED.

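### The plan does not say whether the primary DLMO comparison is adjusted: 9.2.1 names a t-test on change without the minimisation factors, while 9.2 promises covariates chosen by baseline tests

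*Combined protocol and SAP*

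**What the plan says.** Section 2.2.1 defines the endpoint: "The primary endpoint is change in time of DLMO from pre- to post-treatment". Section 9.2.1 computes that change in minutes for each participant and then states "A 2-tailed t-test will evaluate the difference between the change in DLMO between the two groups". It names no covariate.

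Section 9.2, the parent of both 9.2.1 and 9.2.2, has the arms compared on pre-treatment variables by t-tests, chi-square tests and Fisher's exact tests. It continues: "Variables that emerge as potential confounders from this analysis will be controlled for in the final analyses". It does not list the variables, define what counts as emerging, or say which analyses are the final ones.

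Section 5.1 allocates by minimisation: "Assignment to condition will be balanced by age and baseline sleep onset time on free days". Neither factor appears as a covariate in 9.2, 9.2.1, 9.2.2 or the synopsis. The synopsis mentions only t-tests and linear mixed models, and 9.2.2 assigns the mixed models to the secondary sleep variables.

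**The concern.** There are three linked problems.

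- **Undefined primary result.** If the covariate rule in 9.2 covers the primary endpoint, the t-test in 9.2.1 is not the primary analysis. If it does not, 9.2 should say so. Two analysts could follow this plan and report different primary results.
- **A selection rule that looks in the wrong place.** After randomised allocation, between-arm baseline tests detect only chance imbalance. They say nothing about whether a variable predicts outcome. Minimisation suppresses imbalance in age and sleep onset, so the rule is least likely to pick the two variables the design itself treats as important.
- **Some lost precision.** A change score subtracts baseline DLMO with a fixed slope of 1. ANCOVA estimates the slope, and its variance is smaller unless the pre-post correlation is high. Leaving out the minimisation factors also makes the t-test somewhat conservative when they predict outcome.

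The t-test on change is not biased. What is at stake is clarity about the primary result and a modest amount of power in a trial of 50.

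**Working it through.** **Inputs from the documents.** Difference 1 h (60 min), 90% power, alpha 0.05, 23 per group required and 25 planned (9.1). Two-sided test (9.2.1). Two minimisation factors (5.1).

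**The plan's own figure.** Section 9.1 says "the sample size required to detect this change at 90% power with an alpha of 0.05 is 23 per group". No SD is given, so the 23 cannot be reproduced. It can only be inverted. Setting two-sided noncentral-t power to 0.90 at n = 23, difference 60 min, df = 44, gives an SD of change of 61.4 min (1.02 h).

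**Closed form.** The t-test has SE = SD × √(2/n) and df = 2n − 2. For ANCOVA on baseline DLMO with equal pre and post variances, Var(ANCOVA)/Var(change) = (1 + rho)/2 and df = 2n − 3. Rho is not in the documents, so 0.5, 0.7 and 0.9 are assumed.

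At n = 25 the t-test has SE = 61.4 × √(2/25) = 17.4 min, noncentrality 60/17.4 = 3.46 and power 92.3%. At rho 0.5 the ANCOVA SE is 17.36 × √0.75 = 15.0 min, noncentrality 3.99 and power 97.4%.

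| Power for 60 min | t-test | ANCOVA, rho 0.5 | rho 0.7 | rho 0.9 |
|---|---|---|---|---|
| 25 per group | 92.3% | 97.4% | 95.6% | 93.5% |
| 17 per group | 78.9% | 89.0% | 84.9% | 80.8% |

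The second row reflects possible missing pairs. Section 1.2 reports, for adults with DSWPD, "high compliance, as 83% of the in-home samples were valid", and the endpoint needs two usable DLMOs per person. If 83% applies to each DLMO and failures are independent, 0.83² = 0.69 of participants are evaluable, or about 17 per group. Both conditions are assumptions.

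**Simulation with minimisation** (8,000 trials per cell, Monte Carlo SE at most 0.5 points, SD of change 61.4 min). Assumed, not in the documents:

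- biased coin 0.9, with two age and three sleep-onset categories;
- sleep onset correlated 0.8 with baseline DLMO, and age unrelated to outcome;
- ten candidate baseline variables (baseline DLMO, sleep onset, age and seven irrelevant ones), selected at p < 0.05;
- pairs missing at random.

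The proposed model contains arm, baseline DLMO, age and sleep onset. Entries are power at rho 0.5 / 0.7 / 0.9.

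| Evaluable | t-test on change | Proposed model | Gain (points) | Covariates chosen by baseline tests |
|---|---|---|---|---|
| 100% | 93.7 / 93.2 / 92.8 | 96.8 / 95.0 / 92.7 | 3.1 / 1.8 / −0.1 | 92.6 / 92.0 / 91.5 |
| 83% | 87.6 / 87.1 / 86.5 | 92.8 / 89.6 / 85.9 | 5.2 / 2.5 / −0.6 | 84.5 to 85.7 |
| 69% | 79.2 / 78.6 / 78.0 | 85.8 / 81.4 / 76.9 | 6.6 / 2.8 / −1.1 | 75.2 to 76.4 |

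**What the selection rule picks.** With everyone evaluable it selected each minimised factor in under 0.1% of trials, baseline DLMO in 0.7%, each irrelevant variable in 5.1%, and something in 31%. The last figure follows from the seven irrelevant variables: 1 − (1 − 0.051)⁷ = 31%. For independent tests at 0.05 in general, 1 − 0.95ᵏ gives 23% for 5 tests, 40% for 10 and 64% for 20.

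**Type I error, same simulation.** t-test 3.9 to 4.7%, selection rule 3.9 to 4.7%, proposed model 4.9%, better of t-test and selection rule 4.4 to 5.2%.

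**A second simulation under other assumptions** (6,000 trials per setting, coin 0.8) let the two minimisation factors explain a share R² of the variance in change. At R² = 0 / 0.2 / 0.4, t-test type I error was 5.5 / 3.7 / 2.8%. With both factors in the model it was 5.5 / 5.0 / 5.2%. Taking the smaller p-value of the t-test and the selected-covariate model gave 6.1 / 4.2 / 3.3%. The selection rule lost 1.6 to 1.9 points of power against the t-test.

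**The case against.** The strongest reply is that 9.2.1 names its test outright, the synopsis also mentions no covariates, and the sentence in 9.2 is a general preamble. One clarifying sentence would then be enough, and replacing a valid, unbiased test is a matter of preference. The unadjusted reading is the more natural one. Still, 9.2 heads 9.2.1 and does not exempt it, and the synopsis does not settle which analyses the covariate rule covers.

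Several narrower points stand:

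- The gain depends on rho. With all 50 evaluable it is 3.1, 1.8 and −0.1 points, and the upper end of the 2 to 7 range needs both rho 0.5 and 31% missing. At rho 0.9 missing pairs favour the t-test.
- The 83% figure refers to samples, not to participants or pairs. Section 1.2 also reports 92% and 98% in other groups. ANCOVA needs the same pairs, so it recovers no one. The reassignment allowed in 5.1 was not simulated.
- Where age and sleep onset predict nothing beyond baseline DLMO, adding them costs 0.4 to 2.2 points of power against ANCOVA on baseline DLMO alone and does not improve type I error. Their benefit appears only if they do predict outcome, as in the second simulation. That is plausible for sleep onset, because section 6.2 uses it to set the initial administration time in the E-DLMO arm.
- The 31% figure reflects an assumed number of baseline variables.

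These points limit the size of the benefit. They do not rescue the covariate rule, which lost power at every rho and missingness level in the first simulation, or remove the ambiguity.

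**Conclusion.** The concern holds. The plan names an unadjusted t-test, omits both minimisation factors, and separately promises covariates chosen by baseline tests without saying whether the primary analysis is included.

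The size is modest. The proposed model gains about 2 to 7 points of power at rho 0.5 to 0.7 and nothing, or a loss of about 1 point, at rho 0.9. The selection rule costs 1 to 3 points against the plain t-test. Freedom to choose between the two readings takes type I error to 6.1% in the least favourable setting with minimisation, and to 5.2% or less in the main simulation.

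These figures rest on the back-solved SD and on assumed values for rho, the missing-data rate, the minimisation settings and the number of baseline variables. The textual inconsistency depends on none of them. The change should be made, mainly for clarity and secondly for precision. Confidence is medium.

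**What to change.** Replace section 9.2.1 with:

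> Primary analysis: linear regression of post-treatment DLMO (minutes) on arm, baseline DLMO, age and baseline free-day sleep onset time, reporting the adjusted mean difference with its 95% CI. The two-tailed t-test on change in DLMO is a sensitivity analysis.

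In section 9.2, delete the sentence on controlling for variables found by the baseline comparison, and present baseline data descriptively. The endpoint in 2.2.1 can stay: with baseline DLMO in the model, subtracting it from the outcome changes only its own slope, by 1, and leaves the arm coefficient the same. Fix the model before outcome data are seen by arm.

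If the sponsor prefers to keep the t-test, the minimum is to state that it alone gives the primary result and still delete the selection rule.

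No new data are required. Section 7.1 says "all eligible participants (regardless of group assignment) will undergo in-home salivary DLMO collection at pre- and post-treatment", and age and sleep onset are already used at allocation. The model uses three degrees of freedom, plus the 0.4 to 2.2 points of power noted above if the two factors turn out not to be prognostic. The administrative cost is an amendment; section 12.2 says "Any amendments to the protocol must be reviewed and approved by IRBMED".

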#### ***9.2.2 Analysis of Secondary Endpoints***

Linear mixed models using a repeated measures group X time (weeks of study) model will be used to determine between-group main effects and interactions with week of study for the following actigraphy and sleep diary variables: sleep onset time, initial sleep latency, total sleep time, sleep offset time, wake after sleep onset, and sleep efficiency. T-tests (2-tailed) will compare group differences in the change from pre- to post-treatment on the following: ESS score; SF-12 score; MFI-20 score.

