Variables: Time of DLMO in minutes; Epworth Sleepiness Scale score (ESS); Multidimensional Fatigue Inventory score (MFI-20); Short-Form Health Survey (SF-12);

from diary and actigraphy: total sleep time, initial sleep latency, sleep onset time, sleep offset time.

**Statistical Methods:** Statistical analyses will include 2-tailed t-tests and linear mixed models to test group differences on outcomes.

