### **1.3 Hypothesis**

#### Specific Aims

Aim 1: Compare pre- to post-treatment changes in DLMO in M-DLMO vs. E-DLMO conditions.

Hypothesis 1: Participants in the M-DLMO condition will show greater improvements in DLMO (i.e., greater advance of DLMO) relative to participants in the E-DLMO condition after 4 weeks of exogenous melatonin.

Aim 2: Compare pre- to post-treatment changes in objective and subjective sleep parameters and daytime symptoms in M-DLMO vs. E-DLMO conditions.

Hypothesis 2: Participants in the M-DLMO condition will show greater improvements in objective (per wrist actigraphy) and subjective (per daily sleep-wake diary) sleep parameters (specifically, total sleep time, initial sleep latency, sleep onset time, sleep offset time) after 4 weeks of exogenous melatonin. They will also show greater improvements in daytime symptoms.

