### **2.2.2 Secondary Endpoint**

Secondary endpoints include:

- Change in sleep parameters per wrist actigraphy and sleep diary (specifically, total sleep time, initial sleep latency, sleep onset time, sleep offset time) from pre- to post-treatment.
- Change in daytime symptoms and functioning (as assessed by the Epworth Sleepiness Scale, Multidimensional Fatigue Inventory-20, Sheehan Disability Scale, Patient Health Questionnaire-9, Generalized Anxiety Disorder-7) from pre- to post-treatment.
- Change in self-report sleep quality and symptoms (as assessed by the Pittsburgh Sleep Quality Index, Morningness Eveningness Questionnaire, PROMIS-Sleep Disturbance scale, PROMIS-Sleep Related Impairment scale).

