## 7.2 Secondary Assessments

Secondary Assessments: 1. Change from pre- to post-treatment in sleep parameters (total sleep time, initial sleep latency, sleep onset time, sleep offset time) measured using wrist actigraphy and daily sleep diaries; 2. Change in daytime symptoms and functioning (Epworth Sleepiness Scale, Multidimensional Fatigue Inventory-20, Sheehan Disability Scale, Patient Health Questionnaire-9, Generalized Anxiety Disorder-7,) from pre- to post-

treatment, 3. Change in self-report sleep quality and symptoms (as assessed by the Pittsburgh Sleep Quality Index, , Morningness Eveningness Questionnaire, PROMIS-Sleep Disturbance scale, PROMIS-Sleep Related Impairment scale).

**Wrist Actigraphy Assessments:** The Actiwatch Spectrum Plus will be worn by participants daily throughout the protocol for wrist actigraphy monitoring to approximate objective sleep/wake patterns. The Actiwatch Spectrum Plus is a kinesiology ambulatory recorder manufactured by Philips Respironics (Bend, Oregon), and is exempt from FDA premarket submission. Actigraphy data will be scored using Actiware®-Sleep software following standard scoring procedures (Patel et al. 2015).

**Sleep Diary Assessments:** Participants will maintain daily self-report sleep-wake diaries daily throughout the treatment protocol.

**Daytime Symptoms Assessments:** Participants will complete the self-report questionnaires (Epworth Sleepiness Scale, Multidimensional Fatigue Inventory-20, Sheehan Disability Scale, Patient Health Questionnaire-9, Generalized Anxiety Disorder-7,) to assess daytime symptoms.

**Sleep Quality and Symptoms:** Participants will complete the self-report questionnaires (the Pittsburgh Sleep Quality Index, Morningness Eveningness Questionnaire, PROMIS-Sleep Disturbance scale, PROMIS-Sleep Related Impairment scale) to assess sleep quality and symptoms.

**Exploratory Assessment:** Conners Adult ADHD Rating Scale-Short Form (Change from pre- to post-treatment)

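### Section 9.2.2 names a test for only two of the nine listed secondary questionnaires, tests SF-12 although it is not a listed endpoint, and leaves open which sleep-model term, with what role for baseline, tests the pre-to-post change

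*Combined protocol and SAP*

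**What the plan says.** **Questionnaires.** Section 2.2.2 lists five daytime scales: ESS and then "Multidimensional Fatigue Inventory-20, Sheehan Disability Scale, Patient Health Questionnaire-9, Generalized Anxiety Disorder-7". It adds four sleep-quality scales: PSQI and, in the words that 7.2 repeats, "Morningness Eveningness Questionnaire, PROMIS-Sleep Disturbance scale, PROMIS-Sleep Related Impairment scale". Table 1 schedules the self-report measures at baseline and at the final visit only.

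The analysis text in 9.2.2 reads: "T-tests (2-tailed) will compare group differences in the change from pre- to post-treatment on the following: ESS score; SF-12 score; MFI-20 score". The synopsis variable list agrees with that shorter set: after ESS it gives "Multidimensional Fatigue Inventory score (MFI-20); Short-Form Health Survey (SF-12". On methods, the synopsis says "Statistical analyses will include 2-tailed t-tests and linear mixed models to test group differences on outcomes", without tying either method to an endpoint.

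**Sleep variables.** Aim 2 is to "Compare pre- to post-treatment changes in objective and subjective sleep parameters and daytime symptoms in M-DLMO vs. E-DLMO conditions", and 2.2.2 defines the sleep endpoints as pre-to-post change in four parameters, each by actigraphy and by diary. Section 9.2 prepares the data: "Weekly averages will be calculated for total sleep time, initial sleep latency, sleep onset time, and sleep offset time". Section 9.2.2 then fits a repeated-measures group-by-week mixed model to six variables, adding wake after sleep onset and sleep efficiency. Those models "will be used to determine between-group main effects and interactions with week of study". Neither section says whether the baseline week is a level of time, a covariate, or left out.

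**The concern.** The endpoint sections and the analysis section do not describe the same set of outcomes. An analyst following 9.2.2 literally would test one scale that is not a declared endpoint and would find no instruction for seven that are. Those seven include all four sleep-quality scales, which form one of the three groups of secondary endpoints.

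For the sleep variables the gap is in the estimand. A group main effect averages the arm difference over the modelled weeks. An interaction asks whether that difference changes between weeks. Neither is tied to the pre-to-post change that 2.2.2 declares, and the meaning of both depends on whether baseline is in the model. Two competent analysts could report different quantities for the same endpoint and both claim to have followed the plan.

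**Working it through.** The plan gives no figure on this point to reproduce. The check is a comparison of lists, followed by short arithmetic on what each model term estimates.

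**1. Lists side by side**

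| Outcome | 2.2.2 and 7.2 | Synopsis variables | Named in 9.2.2 |
|---|---|---|---|
| ESS, MFI-20 | yes | yes | yes (t-test on change) |
| Sheehan, PHQ-9, GAD-7 | yes | no | no |
| PSQI, MEQ, two PROMIS scales | yes | no | no |
| SF-12 | no | yes | yes (t-test on change) |
| Four sleep parameters | yes | yes | yes (mixed model) |
| Wake after sleep onset, sleep efficiency | no | no | yes (mixed model) |

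Listed questionnaires: 5 + 4 = 9. Named in 9.2.2: 2. Not named: 9 − 2 = 7, made up of 3 of the 5 daytime scales and all 4 sleep-quality scales. The last row is also missing from the four weekly averages in 9.2.

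**2. What each sleep-model term estimates**

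Let D be the difference between arms in treatment week 4, with no difference at baseline. Weeks 1 to 4 are counted from Visit 1. Two shapes are assumed for illustration.

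- Linear divergence, differences (0, 0.25, 0.50, 0.75, 1.00) × D at baseline and weeks 1 to 4. Main effect with baseline as a model week: 2.50/5 = 0.50 D. Without it: 2.50/4 = 0.625 D. Week 4 minus baseline: 1.00 D. Week 4 minus week 1: 1.00 − 0.25 = 0.75 D.
- Full difference from week 1, differences (0, 1, 1, 1, 1) × D. Main effect with baseline: 4/5 = 0.80 D. Without it: 4/4 = 1.00 D. Week 4 minus baseline: 1.00 D. Week 4 minus week 1: 0, so an interaction fitted to weeks 1 to 4 only is zero.

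The main effect thus runs from 0.50 D to 1.00 D. In the second pattern the interaction either carries the whole effect or none of it, depending only on whether baseline is modelled.

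**3. Change score against ANCOVA for the questionnaires**

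Assume equal pre and post variance σ² and pre-post correlation ρ.

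- Variance of a change score: 2σ²(1 − ρ).
- Residual variance after baseline adjustment: σ²(1 − ρ²).
- Ratio: (1 − ρ²) / [2(1 − ρ)] = (1 + ρ)/2, ignoring the one degree of freedom spent on the covariate.

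At ρ = 0.3, 0.5 and 0.7 the ratio is 0.65, 0.75 and 0.85. The documents give no correlation, so this range is an assumption. With unequal standard deviations σ₀ (pre) and σ₁ (post), the change-score variance exceeds the ANCOVA variance by (σ₀ − ρσ₁)². This is never negative, so the direction of the gain does not depend on equal variances; its size does.

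**4. Which nights make up the final week**

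Table 1 puts the final visit at Day 28 with a window of 5 business days either way, about 7 calendar days, so Day 21 to Day 35. The treatment period is 28 days, supplied as 14 + 14 tablets. Suppose tablets run from Day 1 to Day 28 and the final week is taken as the 7 nights before the actual visit. A visit on Day 35 would use Days 28 to 34, with 6 nights after the last tablet. A visit on Day 21 would use Days 14 to 20, mostly week 3. The week should therefore be fixed by treatment day.

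**The case against.** **The seven scales have an obvious default.** They are measured only twice, so a weekly mixed model cannot apply, and the synopsis offers just one other method. This stands: the gap is an incomplete list more than an open choice of method. A reader might infer that the seven scales are not to be analysed, or that the list was shortened to allow selective reporting. The documents support neither reading.

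**SF-12 is not unlisted everywhere.** The synopsis includes it. That is right, and the point is limited to its absence from 2.2.2 and 7.2. Table 1 has only a generic self-report row, so it does not settle whether SF-12 is collected.

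**Baseline can be read into the model.** Table 1 numbers the baseline column as week 0, with diary and actigraphy marked, and 9.2 averages every study week. If baseline is a model week, the interaction is the natural test of pre-to-post change. But 6.2.1 describes the study as lasting four weeks, which points the other way, and 9.2.2 still names the main effect alongside the interaction. The ambiguity is narrowed, not removed.

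**ANCOVA is a preference.** In part, yes: adding seven names to the t-test sentence would close the list gap. A reader might infer that the change-score t-test is wrong. It is valid under randomisation. The case for ANCOVA is precision from data already collected.

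**Error rate.** A reader might also infer that significance on either sleep term would count as success, which would inflate the type I error. The plan states no such rule, so no inflation is claimed.

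**Conclusion.** The point holds as a matter of specification for the secondary endpoints. Seven of nine listed questionnaires have no named test, one scale is tested without being a listed endpoint or assessment, and two sleep variables are modelled without being endpoints or weekly averages. These facts rest on the text alone.

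For sleep, the test of the declared endpoint is not determined. The multiples of D above rest on two assumed effect shapes and no baseline difference; they show that the choice of term and the role of baseline matter, and do not predict the trial's result. No power advantage is claimed for the contrast proposed below.

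The 65% to 85% variance ratio rests on assumed correlations of 0.3 to 0.7 and equal pre and post variances. It is a free gain in precision, not the correction of an error. The primary DLMO comparison in 9.2.1 is unaffected. The change should be made, but the trial's main conclusion does not depend on it.

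**What to change.** 1. **Questionnaires.** In 9.2.2, assign one analysis to every secondary questionnaire, including SF-12 if it is kept: ANCOVA on the post-treatment score, adjusted for the baseline score of the same scale.
2. **Sleep variables.** Use the baseline-week average as a covariate, taken over the last seven days before Visit 1; section 6.2 already uses a seven-day actigraphy window. Model treatment weeks 1 to 4 as outcomes and name one between-arm contrast, in week 4, as the test of each sleep endpoint. Define that week as Days 22 to 28 counted from Visit 1, using available nights, and not by the date of the final visit.
3. **Lists.** Reconcile the synopsis, 2.2.2, 7.2 and 9.2.2. If SF-12 is collected and wanted, add it to 2.2.2 and 7.2; otherwise delete it from the synopsis and 9.2.2. Label wake after sleep onset and sleep efficiency exploratory, and add them to the weekly averages in 9.2.

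The cost is wording in these sections and a little more analysis work. No new data are needed, unless SF-12 is kept and is not already being collected. One limit remains: a participant whose final visit falls at the early edge of the window may have few or no nights in Days 22 to 28 and would contribute through the earlier weeks of the mixed model.
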